14.4 Routine Adverse Event Reporting

All AEs that require expedited reporting via CTEP-AERS must also be reported in routine study data submissions (Adverse Event Form CRF). Routine reporting of all AEs attributed to therapy (possible, probable or definitely), regardless of grade, should be reported on the Adverse Event Form CRF. Similarly, if patients require radiotherapy, post-treatment AEs related to radiation therapy do not require routine reporting. All Grade 5 events, regardless of attribution to therapy, must be reported in the Adverse Event and Death Forms in AdvantageEDC_{SM}.

14.5 Secondary Malignancy

A secondary malignancy is a cancer caused by treatment for a previous malignancy (e.g., treatment with investigational agent/intervention, radiation or chemotherapy). A secondary malignancy is not considered a metastasis of the initial neoplasm.

Acute myeloid leukemia (AML)/Myelodysplastic syndrome (MDS) events must be reported via CTEP-AERS (in addition to your routine AE reporting mechanisms). In CTCAE v4.0, the event(s) may be reported as either: 1) Leukemia secondary to oncology chemotherapy, 2) MDS, or 3) Treatment-related secondary malignancy. Whenever possible, the CTEP-AERS report should include the following: tumor pathology; history of prior tumors; prior treatment/current treatment including duration; any associated risk factors or evidence regarding how long the tumor may have been present; when and how the tumor was detected; molecular characterization or cytogenetics of the original tumor (if available) and of any new tumor; and tumor treatment and outcome, if available. These events should be reported for the duration of the study treatment and during the protocol-specified follow-up period.

15.0 EFFICACY AND SAFETY MEASUREMENTS

15.1 Efficacy Measurements

All subjects will be evaluated for clinical response by physical examination prior to receiving treatment on each cycle. The exam should occur within 3 days prior to the start of each cycle, but may occur on Day 1 of cycle.

All subjects will be evaluated for clinical response by imaging studies after by FDG-PET/CT at the completion of cycle 2 and at the completion of therapy (See Section 10.6.1).

15.2 Response Assessment

Response is currently assessed on the basis of clinical, radiologic, and pathologic (i.e., bone marrow) criteria.

15.2.1 Definition of Response

The response definitions used for this study are the 2007 Cheson criteria. A major distinction in the 2007 criteria is that PET/Gallium studies are used to facilitate the distinction between persistent tumor and scar/fibrosis.

15.2.2 Complete Response (CR)

- 1. Complete disappearance of all detectable clinical evidence of disease and disease-related symptoms if present before therapy.
- 2a. Typically FDG-avid lymphoma: In patients with no pretreatment PET scan or when the PET scan was positive before therapy, a post-treatment residual mass of any size is permitted as long as it is PET negative.
- 2b. Variably FDG-avid lymphomas/FDG avidity unknown: In patients without a pretreatment PET scan, or if a pretreatment PET scan was negative, all lymph nodes and nodal masses must have regressed on CT to normal size (1.5 cm in their greatest transverse diameter for nodes > 1.5 cm before therapy). Previously involved nodes that were 1.1 to 1.5 cm in their long axis and more than 1.0 cm in their short axis before treatment must have decreased to 1.0 cm in their short axis after treatment.
- 3. The spleen and/or liver, if considered enlarged before therapy on the basis of a physical examination or CT scan, should not be palpable on physical examination and should be considered normal size by imaging studies, and nodules related to lymphoma should disappear. However, determination of splenic involvement is not always reliable because a spleen considered normal in size may still contain lymphoma, whereas an enlarged spleen may reflect variations in anatomy, blood volume, the use of hematopoietic growth factors, or causes other than lymphoma.
- 4. If the bone marrow was involved by lymphoma before treatment, the infiltrate must have cleared on repeat bone marrow biopsy. The biopsy sample on which this determination is made must be adequate (with a goal of >20 mm unilateral core). If the sample is indeterminate by morphology, it should be negative by immunohistochemistry.
- 15.2.3 Partial Response (PR) requires all of the following:
 - 1. At least a 50% decrease in sum of the product of the diameters (SPD) of up to six of the largest dominant nodes or nodal masses. These nodes or masses should be selected according to all of the following: they should be clearly measurable in at least two perpendicular dimensions; if possible they should be from disparate regions of the body; and they should include

mediastinal and retroperitoneal areas of disease whenever these sites are involved.

- 2. No increase should be observed in the size of other nodes, liver, or spleen.
- 3. Splenic and hepatic nodules must regress by 50% in their SPD or, for single nodules, in the greatest transverse diameter.
- 4. With the exception of splenic and hepatic nodules, involvement of other organs is usually assessable and no measurable disease should be present.
- 5. Patients who achieve a CR by the above criteria, but who have persistent morphologic bone marrow involvement will be considered partial responders. When the bone marrow was involved before therapy and a clinical CR was achieved, but with no bone marrow assessment after treatment, patients should be considered partial responders.
- 6. No new sites of disease should be observed.
- 7. Typically FDG-avid lymphoma: for a patient with no pretreatment PET scan or if the PET scan was positive before therapy, the post-treatment PET should be positive in at least one previously involved site.
- 8. Variably FDG-avid lymphomas/FDG-avidity unknown: if a pretreatment PET scan was negative, CT criteria should be used.
- 15.2.4 Stable Disease (SD) is defined as the following:
 - 1. A patient is considered to have SD when he or she fails to attain the criteria needed for a CR or PR, but does not fulfill those for progressive disease (see Relapsed Disease [after CR]/Progressive Disease [after PR, SD]) below.
 - 2. Typically FGD-avid lymphomas: the PET should be positive at prior sites of disease with no new areas of involvement on the post- treatment CT or PET.
 - 3. Variably FDG-avid lymphomas/FDG-avidity unknown: if the pretreatment PET was negative, there must be no change in the size of the previous lesions on the post-treatment CT scan.
- 15.2.5 Relapsed Disease (after CR)/Progressive Disease (after PR, SD):
 - 1. Lymph nodes should be considered abnormal if the long axis is more than 1.5 cm regardless of the short axis. If a lymph node has a long axis of 1.1 to 1.5 cm, it should only be considered abnormal if its short axis is more than 1.0. Lymph nodes 1.0 x 1.0 cm will not be considered as abnormal for relapse or progressive disease.
 - 2. Appearance of any new lesion more than 1.5 cm in any axis during or at the end of therapy, even if other lesions are decreasing in size. Increased FDG uptake in a previously unaffected site should only be considered relapsed or progressive disease after confirmation with other modalities. In patients with no prior history of pulmonary lymphoma, new lung nodules identified by CT are mostly benign. Thus, a therapeutic decision should not be made solely on the basis of the PET without histologic confirmation.
 - 3. At least a 50% increase from nadir in the SPD of any previously involved nodes, or in a single involved node, or the size of other lesions (e.g., splenic or hepatic nodules). To be considered progressive disease, a lymph node with a diameter of the short axis of less than 1.0 cm must increase by 50% and to a size of 1.5 x 1.5 cm or more than 1.5 cm in the long axis. At

least a 50% increase in the long est. diameter of any single previously identified node more than 1 cm in its short axis. Lesions should be PET positive if observed in a typical FDG-avid lymphoma or the lesion was PET positive before therapy unless the lesion is too small to be detected with current PET systems (< 1.5 cm in its long axis by CT).

15.2.6 Recurrent Disease

Recurrent Disease is defined as the appearance of tumor following documentation of a complete remission.

15.2.7. Time to Response

Time to Response is defined as time from the first dose of chemotherapy until documentation of first response.

15.2.8. Time to Progression

Time to Progression is defined as time from initiation of chemotherapy to documentation of first progression.

15.2.9 Response Duration

Response Duration is defined as the time from first documentation of response to documentation of first progression.

15.3 Safety Measures

All AE will be monitored by ongoing review of reported adverse events by the protocol chair and the AMC Operations and Data Management Center, and will be discussed during the monthly investigators' Lymphoma Working Group conference calls (see Section 12.4 for rules for early study termination).

16.0 STATISTICAL CONSIDERATIONS

Statistical analysis will be performed by AMC Statistical Center on pooled data obtained by French participants and US participants.

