3.1 Eligibility Criteria

- $\begin{array}{c} 3.1.1 \quad \text{Age} \geq 18 \text{ years. Because no dosing or adverse event data are currently available on the use of brentuximab vedotin in combination with AVD in patients <18 years of age, children are excluded from this study. \end{array}$
 - _ 3.1.2 HIV positive. Documentation of HIV-1 infection by means of any one of the following:
 - Documentation of HIV diagnosis in the medical record by a licensed health care provider;
 - Documentation of receipt of ART by a licensed health care provider;
 - HIV-1 RNA detection by a licensed HIV-1 RNA assay demonstrating > 1000 RNA copies/mL;
 - Any licensed HIV screening antibody and/or HIV antibody/antigen combination assay confirmed by a second licensed HIV assay such as a HIV-1 Western blot confirmation or HIV rapid multispot antibody differentiation assay.

NOTE: A "licensed" assay refers to a US FDA-approved assay, which is required for all IND studies.

- 3.1.3 Histologic diagnosis of CD30-positive classical HL as defined by the 2008 WHO Classification of Hematological diseases. Nodular lymphocyte predominant Hodgkin Lymphoma is not eligible.
- _____ 3.1.4 Stage II, III, or IV disease as defined by the Ann Arbor Staging System.
- 3.1.5 Participants must have previously untreated HIV-cHL, with the exception of up to 14 consecutive days of steroids, emergency radiation, or 1 prior cycle of cyclophosphamide to reduce tumor burden and improve hyperbilirubinemia in the setting of lymphoma related liver involvement.
 - $_$ 3.1.6 Normal baseline cardiac ejection fraction $\ge 50\%$.

- 3.1.7 Serum creatinine of ≤ 1.5 mg/dL. If creatinine >1.5 mg/dL, creatinine clearance must be ≥ 60 mL/minute.
- $_$ 3.1.8 ANC ≥ 1000/µL and platelets ≥ 75,000/µL unless related to bone marrow involvement by HIV-cHL.

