11.0 STATISTICAL CONSIDERATIONS

11.1 Study Design/Endpoints

This multicenter, Phase I/II open label study will determine the safety and tolerability of participants with stage II/IV HIV-associated Hodgkin Lymphoma and evaluate the treatment effect of AVD in addition to brentuximab vedotin (SGN-35). The primary objective of the Phase I portion of the study is to identify the maximal tolerated doses of brentuximab vedotin when combined with the AVD chemotherapy regimen in HIV participants with advanced stage Hodgkin lymphoma. The primary objective of the Phase II portion of the study is to establish an estimate of the two-year progression-free survival for participants using brentuximab vedotin plus AVD regimen with HIV-associated advanced stage Hodgkin lymphoma.

Secondary objectives include:

- 1. To evaluate toxicity of AVD and brentuximab vedotin with HAART.
- 2. To estimate the partial response (PR) rate, complete response (CR) rate, overall survival (OS), event free survival at 2 and 5 years.
- 3. To evaluate effect of AVD and brentuximab vedotin on CD4 and CD8 counts after cycle 1, 4, at the end of therapy, and every 3 months after treatment completion for one year.
- 4. To investigate the prognostic value of FDG-PET/CT scans at baseline, after cycle 2, and at treatment completion, with respect to 2-year progression free survival.
- 5. To evaluate HAART status at baseline and to correlate this with tumor response to therapy and OS and PFS.
- 6. To characterize the histologic subtypes in HIV-HL in the highly active antiretroviral therapy (HAART) era.
- 7. To assess the neurotoxicity of HAART in combination with AVD and brentuximab vedotin.
- 8. To evaluate effect of AVD and brentuximab vedotin on viral load after cycles 1, 4, at completion of therapy, and every 3 months after treatment completion for one year.
- 9. To perform pharmacokinetic and immunogenicity studies to determine drug levels during therapy (see Section 10.0 and Appendix IX).
- 10. To perform miRNA profile analysis on the HIV-HL tumor specimens and to correlate miRNA expression with OS, PFS, tumor response to therapy, histologic subtype of HIV-HL, and HIV disease characteristics (see Section 10.0 and Appendix VIII).
- 11. To perform tissue microarray analysis on HIV-HL tumor specimens and to correlate the markers studied with OS, PFS, and tumor response to therapy (see Section 10.0 and Appendix VIII).

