11.4 Analysis of Secondary Endpoints

Descriptive summaries and exploratory analyses for secondary objectives will be conducted. Significance for comparisons will be at the p<0.05 level.

Secondary objectives include:

1. To evaluate toxicity of AVD and brentuximab vedotin with HAART.

- 2. To estimate the partial response rate, complete response rate, overall survival (OS), event free survival at 2 and 5 years. To evaluate effect of AVD and brentuximab vedotin on CD4 and CD8 counts after 2 cycles, 6 cycles, and every 3 months after treatment completion for one year.
- 3. To evaluate effect of AVD and brentuximab vedotin on viral load after 2 cycles, 6 cycles, and every 3 months after treatment completion for one year
- 4. To investigate the prognostic value of FDG-PET scans at baseline and after 2 cycles in participant with HIV and HL with respect to 2 year progression free survival.
- 5. To evaluate HAART status at baseline for difference in outcome.
- 6. The characterization of histologic subtypes in HIV-HL in the HAART era.
- 7. To assess additional neurotoxicity in combination with HAART and AVD and brentuximab vedotin.

The frequency of AEs and their severity will be tabulated to evaluate tolerance of AVD and brentuximab vedotin with HAART. Further, binomial probabilities and their 95% confidence intervals will be used to estimate the response rates (i.e., partial response rate, complete response rate, overall response rate) and event free survival at 2 and 5 years of AVD and brentuximab vedotin for a treatment of participants with stage III/IV HIV-associated Hodgkin Lymphoma.

Repeated measures analysis of variance (ANOVA) models will be used to evaluate the effect of AVD and brentuximab vedotin on CD4 counts, CD8 counts and viral load after 1, 4, and 6 cycles, and every 3 months after treatment completion for one year.

Log-rank analysis will be used to investigate the prognostic value of FDG-PET scans at baseline, after 2 cycles and post-therapy in participants with HIV and HL with respect to progression free survival.

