6.0 STUDY OBJECTIVES

6.1 **Primary Objective**

Establish an estimate of the two-year progression free survival for patients with HIVassociated stage III-IV Hodgkin lymphoma when treated using brentuximab vedotin plus the AVD chemotherapy regimen.

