8.1 Inclusion criteria

- Age ≥ 18 years. Because no dosing or adverse event data are currently available on the use of brentuximab vedotin in combination with AVD in patients <18 years of age, children are excluded from this study.
- 2. HIV-1 positive. Documentation of HIV-1 infection by means of one of the following:
 - Documentation of HIV diagnosis in the medical record by a licensed health care provider;
 - Documentation of receipt of ART by a licensed health care provider;
 - HIV-1 RNA detection by a licensed HIV-1 RNA assay demonstration > 1000 RNA copies/mL;
 - Any licensed HIV screening antibody and/or HIV antibody/antigen combination assay confirmed by a second licensed HIV assay such as a HIV-1 Western blot confirmation or HIV rapid multisport antibody differentiation assay.
- 3. Histologic diagnosis of CD30-positive classical HL as defined by the 2008 WHO Classification of Hematological diseases. Nodular lymphocyte predominant Hodgkin Lymphoma is not eligible.
- 4. Stage III or IV disease as defined by the Ann Arbor Staging System.
- 5. Participants must have previously untreated HIV-cHL, with the exception of up to 14 consecutive days of steroids, emergency radiation, or 1 prior cycle of cyclophosphamide to reduce tumor burden and improve hyperbilirubinemia in the setting of lymphoma related liver involvement.
- 6. Normal baseline cardiac ejection fraction $\geq 50\%$.
- 7. Serum creatinine of ≤ 1.5 mg/dL. If creatinine >1.5 mg/dL (133 micromol/L), creatinine clearance must be ≥ 60 mL/minute according to MDRD/Cockroft-Gault formula.
- 8. ANC $\geq 1000/\mu L$ and platelets $\geq 75{,}000/\mu L$ unless related to bone marrow involvement by HIV-cHL.
- 9. Total bilirubin must be < 1.5x the upper limit of normal, unless the elevation of bilirubin is thought to be secondary to Gilbert's syndrome or cART.
 - If, however, the elevated bilirubin is felt to be secondary to antiretroviral therapy, the total bilirubin must be $\leq 3.5 \text{ mg/dL}$ (60 µmol/L), provided that the direct bilirubin is normal and the AST and ALT $\leq 3 \text{ x}$ the upper limit of normal.
 - If the elevation of bilirubin is thought to be secondary to Gilbert's syndrome, the total bilirubin must be $\leq 3x$ the upper limit of normal or the direct bilirubin must be $\leq 1.5x$ the upper limit of normal.

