16.2 Sample Size/Accrual Rate

In the Phase II portion of the study, 51 patients will be enrolled worldwide to estimate the 2-year progression free survival. Sample size calculation is based on providing an estimate of the PFS with a 95% confidence interval $\pm 10\%$ under the hypothesis that 2-year PFS is 85%.

The primary endpoint of the phase II portion will be to estimate the two-year progression-free survival for AVD- brentuximab vedotin which will be done using Kaplan-Meier estimates and corresponding 95% confidence intervals based on standard errors using Greenwood's formula.

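### The French protocol's primary objective is 2-year PFS in stage III-IV, but its only planned primary analysis pools US participants who may be stage II, so no planned analysis estimates that objective

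*Combined protocol and SAP*

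**What the plan says.** **French protocol.** Section 6.1 gives the primary objective: "Establish an estimate of the two-year progression free survival for patients with HIVassociated stage III-IV Hodgkin lymphoma". Section 8.1 enforces that population at entry: "Stage III or IV disease as defined by the Ann Arbor Staging System". Section 16.0 assigns the analysis: "Statistical analysis will be performed by AMC Statistical Center on pooled data obtained by French participants and US participants". Section 16.1 makes the primary analysis a one-sample nonparametric survival analysis. Section 16.2 says "51 patients will be enrolled worldwide to estimate the 2-year progression free survival", with a 95% confidence interval of ±10% if 2-year PFS is 85%, by Kaplan-Meier with Greenwood standard errors. Section 16.3 plans no stratification. Section 7.0 expects 20 of the 51 participants to come from France.

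**AMC protocol.** Criterion 3.1.4 admits "Stage II, III, or IV disease as defined by the Ann Arbor Staging System", and the phase 2 objective in 1.1.2 is for stage II-IV. The statistical section is less settled. Section 11.1 refers to "stage II/IV HIV-associated Hodgkin Lymphoma" and then to advanced stage disease. Section 11.4 describes the response and event-free survival estimates "for a treatment of participants with stage III/IV" disease. French 16.1 and 16.4 also use stage III/IV wording.

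Neither statistical section contains a stage III-IV-only estimate, a subgroup by stage or a French-only analysis.

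**The concern.** The population named in the French objective is not the population in the only primary analysis. French participants are all stage III-IV, but they are analysed together with US participants who may be stage II. The French sponsor has its own EudraCT number and must forward a study report to the authorities and ethics committees (French 19.9). With the plan as written, that report would have a PFS estimate for stage II-IV and none for the objective it states.

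There is also a precision question. The sample-size statement in French 16.2 sits beside an objective limited to stage III-IV, yet fewer than 51 participants would inform that objective if any stage II participants enrol.

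**Working it through.** **1. Populations side by side.**

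| Item | Stage | Source |
|---|---|---|
| French primary objective | III-IV | French 6.1 |
| French eligibility | III or IV | French 8.1, criterion 4 |
| US eligibility | II, III or IV | AMC 3.1.4 |
| AMC phase 2 objective | II-IV | AMC 1.1.2 |
| Primary analysis set | pooled French and US, hence II-IV | French 16.0 to 16.2 |

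The analysis set matches the AMC objective. It matches the French objective only if no US participant is stage II, and nothing in the documents makes that a condition.

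**2. The plan's own figure.** Inputs are 2-year PFS p = 0.85, half-width d = 0.10 and z = 1.96 (French 16.2). Without censoring, the Greenwood standard error equals the binomial one.

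- Required n = z² p(1 − p)/d² = 1.96² × 0.85 × 0.15/0.10² = 48.98, so 49.
- Half-width at n = 51: 1.96 × √(0.1275/51) = 9.8 points.

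The ±10% is reproduced for the pooled 51, with two participants to spare.

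**3. Half-width for stage III-IV.** All 20 French participants are stage III-IV, and 51 − 20 = 31 come from the US. The number of stage II participants among those 31 is not given and there is no cap, so it is varied here. Half-width = 1.96 × √(0.1275/n).

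| Stage II among 31 US (assumed) | Stage III-IV n | Half-width, points |
|---|---|---|
| 0 | 51 | 9.8 |
| 2 | 49 | 10.0 |
| 3 | 48 | 10.1 |
| 6 | 45 | 10.4 |
| 9 | 42 | 10.8 |

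The row with 6 corresponds to about 20% of 31 (0.20 × 31 = 6.2). It follows the background statement in AMC 2.2 and French 5.2 that 80% of patients with HIV-associated classical Hodgkin lymphoma present with stage III/IV. That figure describes presentation in general and does not forecast this trial's accrual.

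**4. Possible shift in the point estimate.** The difference between pooled and stage III-IV PFS is (stage II count/51) × (stage II PFS − stage III-IV PFS). The documents give neither input. As an illustration only, 6 stage II participants and an assumed advantage of 5 to 15 points give 6/51 × 5 = 0.6 to 6/51 × 15 = 1.8 points.

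**The case against.** The strongest reply is that the French protocol presents itself as part of one trial. Its synopsis describes 20 patients in France among the 51 of the AMC protocol, quotes the AMC title with stage II-IV, and 16.0 states the pooling openly. On this view the pooled analysis serves the AMC objective as intended, and the French objective was simply not harmonised. The disclosure point stands, but disclosure is not reconciliation: no text says the French objective gives way to the pooled population, and 16.1 still describes the study as stage III/IV. It is also fair that restating the objective would cure the mismatch without a new analysis, so the fix offers that route.

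Three stronger readings are tempting, and the documents do not support them.

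- **That the stated ±10% is not delivered.** The figure is attached to 51 participants worldwide and is met there. No section promises it for a stage III-IV subset. For that subset it is exceeded only with 3 or more stage II participants, a count the documents do not give.
- **That pooling flatters the result.** Both background sections treat earlier stage as favourable when comparing regimens, but no PFS by stage is given for this regimen. The groups also differ in other ways. French sites require CD4 of at least 100, viral load below 50 copies/ml and DLCO above 70% predicted. US sites accept CD4 of at least 50 and list no viral-load ceiling or DLCO criterion. The direction of any shift is therefore not established.
- **That PFS and response will rest on different participants.** The stage II/IV wording in AMC 11.1 is probably a slip, and the stage III/IV phrase in 11.4 describes the disease treated. Neither defines a second analysis set.

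**Conclusion.** The mismatch is established from the documents without any assumption: the French objective is stage III-IV, the sole primary analysis admits stage II, and no planned estimate answers the French question.

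The numerical consequence is modest. Precision is right for the pooled cohort and not assured for stage III-IV, where the excess over 10 points is 0.1 to 0.8 with 3 to 9 stage II participants, an assumed count. The illustrative shift of 0.6 to 1.8 points is small against a ±9.8-point interval, rests wholly on assumed inputs and has no established sign. This is a single-arm estimation study with no efficacy test for the primary endpoint, so no decision threshold is affected. The reason to act is that the reported estimate should be for the population named in the objective. The loose stage wording is a matter for correction and is not evidence of a second analysis population.

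**What to change.** Choose one of two routes and write it into French section 16.

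1. Pre-specify a Kaplan-Meier estimate of 2-year PFS, with Greenwood interval, in all stage III-IV participants (French plus US stage III-IV) as the analysis for the French primary objective. Keep the pooled stage II-IV estimate for the AMC objective. State the expected half-width for the stage III-IV estimate in 16.2, for example about 10.4 points if n = 45, with the assumed stage II count shown.
2. Alternatively, restate the French primary objective (synopsis and 6.1) as 2-year PFS for stage II-IV in the pooled cohort, making clear that French sites contribute stage III-IV only.

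Under either route, align the wording in AMC 11.1 and 11.4 and French 16.1 and 16.4 so that PFS, response and event-free survival name the same population for each objective.

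The first route costs one additional estimate and a slightly wider stated interval. Stage is already established for eligibility, so it needs no new data or participants. The second costs wording only.
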